7.2. BASELINE TESTING

Subjects who continue to be eligible for this study will then complete baseline testing. Subjective questionnaires will be provided to assess items such as current activity levels, nutrition habits, and lifestyle factors related to health and wellness. Enrolled and randomized subjects will also receive a blood pressure cuff and digital scale to record blood pressure and bodyweight/body composition, respectively. Moreover, subjects will complete electronic calculations to estimate their healthspan and biological age. Finally, subjects will perform three physical fitness tests, including:

- Timed one mile walk/run
- Push-ups (or modified push-ups for women) to exhaustion
- Chair get-ups to exhaustion

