5.2.2 Exclusion Criteria

Subjects presenting any of the following will not be included in the study:

- Currently taking (within the past 30 days) ergogenic dietary supplements including, creatine, protein, amino acids, or stimulants other than caffeine (yohimbe, ephedrine, etc.)
- Currently taking performance enhancing drugs (testosterone or other anabolic-androgenic steroids), human growth hormone, insulin, etc.
- History or current malignancy
- Receiving chemotherapy agents or radiation treatments
- Musculoskeletal disease (muscular dystrophy, arthritis, etc.)
- Recent (<3-months) musculoskeletal injuries
- BMI < 25 or > 35 kg/m²
- Diagnosis of a terminal illness
- Use of prescription medications that influence body composition (i.e., prescription hormone therapies, etc.)
- History of alcohol abuse
- History or current drug abuse
- History or current diagnosis of depression.
- History or current diagnosis of suicidal thoughts/ideation.
- A score of \geq 10 arbitrary units on the PHQ-9 during baseline testing.
- History or current cigarette smoke (including vaping) within the past 14 days from the screening visit
- Insulin-dependent diabetes and/or metformin use
- Chronic kidney or liver disease
- Has significant concurrent illnesses (controlled or uncontrolled), such as diabetes, lupus, epilepsy, or cardiac disorders, hepatitis B/C, HIV, serious mental health illness such as dementia or schizophrenia; psychiatric hospitalization in the past two years,

or other, which in the opinion of the investigator, such conditions might be aggravated as a result of treatment

- The investigator feels that for any reason the subject is not eligible to participate in the study
- History of uncontrolled cardiovascular disease (i.e., myocardial infarction, hypertension, hypercholesterolemia, peripheral vascular disease, other)
- Developmental disability or cognitive impairment that would preclude adequate comprehension of the informed consent form and/or ability to follow study subject requirement and/or record the necessary study measurements
- A family member of the investigator or an employee of the investigator
- Participation in any other investigational study within 30 days prior to consent.

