8. ASSESSMENTS

8.1. Clinical Evaluations

The following clinical evaluations will be conducted during the study review:

- Medical and Medication History An assessment of the subject's health status prior to enrollment to ascertain appropriateness for study participation based on inclusion/exclusion criteria.
- Adverse Event Reporting Investigator examination of the subject and notation of any observations made by the study investigator of a potential adverse event.

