8.2. Assessment of Safety

Self-reported and observed adverse events.

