APPENDIX 1. METHODOLOGIES FOR STUDY OUTCOMES.

Healthspan

A subject's healthspan will be calculated using a proprietary algorithm housed within the prime health application. Briefly, subjects will answer a number of questions regarding their daily health habits, activities, and attitudes. These data will then be placed into a mathematical equation that uses data and statistics from numerous published studies regarding longevity and mortality risk. The outcome number is a subject's estimated "Healthspan," which describes their remaining healthy and active years of life. Importantly, this number can increase or decrease based on a subject's reported lifestyle changes at the end of the intervention period.

Biological Age

The subject's biological age will be estimated using the same proprietary formula used to estimate Healthspan. Briefly, biological age is different from chronological age, which simply reflects the number of years an individual has spent on Earth. Biological age, on the other hand, takes healthy lifestyle factors into account that may prematurely age individuals past their chronological age. Conversely, active and healthy users may find that their biological age is lower than their chronological age. Importantly, this number can increase or decrease based on a subject's reported lifestyle changes at the end of the intervention period.

Lifestyle Risk Factors

These risk factors are assessed by a number of questions pertaining to lifestyle habits that the subject must answer when enrolling in the application. As also extracted from the questionnaire.

Energy and Vitality

These outcome measures are subjective reports based on subject responses to specific questions within the application's questionnaires.

Strength and Endurance

Application users will be required to perform three objective performance tests to get accurate estimates of their healthspan and biological age. These performance tests include: *Upper Body Strength*: Upper body strength will be assessed using the push-ups to failure protocol. Users will be instructed via the application on correct form and technique for push-ups specific to their gender. They will then perform as many push-ups as possible before reaching concentric muscle failure. This number will be reported to assess their upper body strength.

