Endurance: Endurance will be assessed using a one mile walk time. Subjects will perform this assessment at their own determined pace, which is obviously restricted by their physical ability. Running is allowed, but not all subjects will be able to run the full mile. Thus, walking is allowed in this assessment.

Lower Body Strength: Lower body strength will be assessed by chair get-ups to concentric muscle failure. Briefly, subjects must use a chair or a related sturdy surface that reaches the height of their patella. They must fully sit and return to start for each repetition. They will

continue to perform get-ups to concentric muscle failure. This number will be reported to assess their lower body strength.

Body Composition

Body composition will be measured using a previously validated digital scale (RENPHO Smart Scale) that will be delivered to participants upon enrollment in the study. The scale uses bioelectrical impedance to estimate body composition. This involves a low level electrical current being sent through the body; the user cannot feel, hear, or otherwise sense this electrical current. The rate at which the current passes through the body is then input into an algorithm to estimate body composition based on known electrical current rates in human body tissue.

Body composition will also be estimated by questions embedded within the application and a corresponding algorithm.

Blood Pressure

Blood pressure will be measured using a previously validated electronic blood pressure cuff (Oklar Cuff Model C02) that will be delivered to participants upon enrollment in the study. The blood pressure cuff is capable of executing blood pressure measurements with minimal input from the user. Blood pressure is reported as systolic over diastolic, and the user will input these numbers into the application questionnaire.

Daily Steps

Daily steps will be assessed using communication between the Pro2col application and the user's Apple Health or Google Fit application. Apple Health and Google Fit both collect daily step counts by way of accelerometry, gyroscopy, and global positioning systems (GPS) and these data will be transferred to and housed within the Pro2col application.

Depression

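### Minor safety improvement: Section 7.2 lists a home blood pressure reading and then remote fitness tests to failure, but no visible text requires the reading to be checked first or sets a level that holds the subject

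*Combined protocol and SAP*

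**What the plan says.** **Measurement.** Section 7.2 states: "Enrolled and randomized subjects will also receive a blood pressure cuff and digital scale to record blood pressure and bodyweight/body composition, respectively". Appendix 1 (Blood Pressure) adds: "Blood pressure is reported as systolic over diastolic, and the user will input these numbers into the application questionnaire". Section 4.1 lists blood pressure among the primary outcomes.

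**Tests.** Section 7.2 ends its list with a timed mile, push-ups and chair get-ups. Appendix 1 takes two of the three to failure. For push-ups: "They will then perform as many push-ups as possible before reaching concentric muscle failure". For the chair test, subjects "continue to perform get-ups to concentric muscle failure". The mile is self-paced and may be walked. Section 5.1 says that no in-person visits are needed.

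**Eligibility.** Section 5.2.2 excludes subjects with "History of uncontrolled cardiovascular disease (i.e., myocardial infarction, hypertension, hypercholesterolemia, peripheral vascular disease, other". It gives no mmHg value. It also has a discretionary exclusion: "The investigator feels that for any reason the subject is not eligible to participate in the study". Screening in Section 7.1 covers entry criteria, medical and medication history, and demographics and baseline characteristics. It does not name a blood pressure measurement.

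**Safety assessments.** Section 8.1 opens with "The following clinical evaluations will be conducted during the study review" and lists two items: medical and medication history, and adverse event reporting. Section 8.2 consists of "Self-reported and observed adverse events".

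**The concern.** The trial supplies a cuff and collects a reading at the stage when subjects are asked for effort to muscle failure at home. Section 6.5 lists fainting, dizziness and shortness of breath among the risks of physical fitness programs. The eligible population has a BMI of 25 to 35 and averages under 5,000 steps a day.

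The one blood pressure exclusion depends on history. A subject who has never been diagnosed has no history to report, passes screening, and may then record a very high value at home. Nothing in the visible text says who sees that value before the tests or what follows from it. What is at stake is the safety of individual subjects. Both arms do the same tests, so the point implies no bias in the treatment comparison.

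**Working it through.** The plan gives no figure on this point. The check is to follow one subject through the text, and then count the tests concerned.

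**1. Following a subject with undiagnosed high blood pressure.**

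| Step | Text | Does it require a check before the tests? |
|---|---|---|
| Suitability | 5.2: relevant medical conditions are to be considered | No. General, and the reading does not exist yet |
| Screening | 7.1: entry criteria, history, demographics | No blood pressure measurement named |
| Exclusion by history | 5.2.2: uncontrolled hypertension | No. No history, no mmHg level |
| Exclusion by judgement | 5.2.2: any reason | Permits action; nobody is told to look |
| Home reading | 7.2 and Appendix 1: subject enters it in the app | No reviewer, level or action |
| Continuing eligibility | 7.2: subjects who remain eligible go on | No blood pressure criterion to apply |
| Oversight | 6.5: general supervision | No check named |
| Withdrawal | 7.5: at discretion, for safety | Permits action; no trigger |
| Safety assessment | 8.1, 8.2 and 9: history and adverse events | Not tied to the time before the tests |
| Data review | 12.2, 12.3: transcription and CRF approval | No timing relative to the tests |

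Every row either allows action or acts at an unspecified time. None requires the reading to be seen before the tests.

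**2. Comparison with a rule the protocol already has.** A baseline PHQ-9 score of 10 or more is an exclusion (5.2.2), and a staff member then contacts the subject (Appendix 1). A numeric stop at baseline with remote follow-up is therefore already part of this design.

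**3. Order of events.** Section 5.1 assigns subjects after baseline testing. The 7.2 device sentence speaks of subjects already randomized, and the 7.1 consultation, placed before baseline testing, covers condition assignment. Appendix 1 has the devices delivered on enrollment. A hold before assignment fits 5.1 and Appendix 1, but not 7.1 and 7.2 as worded.

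**4. Number of baseline tests to failure.** There are two per subject (push-ups and get-ups). Section 5.1 gives 50 to 200 subjects.
- Lower: 2 × 50 = 100
- Upper: 2 × 200 = 400

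**5. Expected number held, for costing only.** The share p above a limit is not in the documents, and the limit is not yet set. Assuming p = 0.5%, 1% or 3%, expected number = n × p:

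| n | 0.5% | 1% | 3% |
|---|---|---|---|
| 50 | 0.25 | 0.5 | 1.5 |
| 200 | 1 | 2 | 6 |

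These are averages under an assumption, not upper bounds, and they say nothing about how often harm would occur.

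**The case against.** The protocol is not silent on the subject. It excludes uncontrolled hypertension by history and cardiac disorders whether controlled or not, limits age to 21 to 60, requires freedom from disease, allows modified push-ups for women and lets subjects walk the mile. Section 9 counts clinically significant signs as adverse events and collects them from consent. Section 12.3 makes the investigator responsible for CRF review. Staff would therefore see the readings at some point. This stands, and it lowers the risk. It does not place a review before the tests.

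Some material is not visible. Section 7 refers to a schedule of study visits in Appendix 1, which in the supplied text holds only outcome methods. The in-app test instructions are also not shown. A check could sit in either place. Nothing in the text points to one, but this limits confidence.

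A reader might infer that subjects are likely to be harmed, or that the 100 to 400 tests measure that harm. The documents do not support this. Section 6.5 gives general risks of fitness programs, no passage links a resting blood pressure to injury in these tests, and no event rate is given.

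A reader might also infer that the same hold must apply at post-testing, because Section 7.4 repeats the sequence. That does not follow. Fitness scores and blood pressure are both primary outcomes. A hold at post-testing would make the first missing according to the second, possibly at different rates by arm, and Section 10.3.1 has no method for missing data.

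**Conclusion.** The gap is real and modest. No visible text requires staff or the app to check the home reading before the remote baseline tests, or sets a level at which a subject is held. General eligibility, discretion, oversight and reporting provisions permit action without prompting it. This is more than missing detail: the protocol treats uncontrolled hypertension as disqualifying, yet its steps can let an undiagnosed subject through when no staff are on site.

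It covers 100 to 400 baseline tests to failure, and the size of the risk in those tests cannot be derived from the documents. The conclusion rests on reading the visible text and on the assumption that the visit schedule and in-app instructions hold no such rule. It is a cheap safety improvement for the sponsor to consider.

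**What to change.** **In Section 7.2**
- Require the cuff reading, repeated if high, to be entered and checked by study staff or by an app rule before any baseline fitness test. The check should not depend on subjects identifying themselves.
- State a systolic/diastolic hold limit set by the investigator.
- A subject above the limit does no fitness test and is not randomized until the investigator decides. A subject not cleared is a screen failure under the existing investigator-judgement exclusion in 5.2.2.
- Delete the words saying that device recipients are already randomized, so that the section matches the order in 5.1.

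**In Section 7.1**
- Move the condition-assignment part of the consultation to after baseline testing.

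**In Section 7.4**
- Leave any post-test hold to the investigator as a trade-off between safety and complete outcome data. If one is used, report the held subjects by arm, because the missing fitness scores would depend on an outcome.

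**Cost.** One investigator decision and short edits to 7.1 and 7.2. Randomization waits for device delivery. Existing staff make occasional contacts, and some devices go to subjects who are not cleared. Under the assumed shares, the expected number held is 0.25 to 1.5 of 50, or 1 to 6 of 200, and those not cleared are some part of these.

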4. OUTCOMES MEASURE

- 4.1. Primary Outcomes these measures will be taken at week 0 (pre) and week 7 (post)
 - Healthspan, as assessed via a digital score within the application software.
 - **Biological Age**, as assessed via an algorithm sourced within the application.
 - Lifestyle Risk Factors, as assessed via questionnaires within the application.
 - Energy and Vitality, as assessed via questionnaires within the application.
 - Strength and Endurance, as assessed by performance measures including a timed mile walk/run, push-ups to exhaustion, and chair get-ups to exhaustion.
 - Body Composition, as assessed via a previously validated digital scale.
 - Blood Pressure, as assessed via an electronic blood pressure cuff.
 - Lifestyle Habits, as assessed by specific interfaces within the application and guided by an AI "coach."
 - **Daily Steps**, as collected via the Apple Health or Google Fit application on the subject's pre-existing personal device.

4.2. Secondary Outcomes – these measures will be taken at week 0 (pre) and week 7 (post)

- **Depression**, as assessed by the previously validated PHQ-9 subjective questionnaire.
- Quality of Life, as assessed by the previously validated SF-36 subjective questionnaire.

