5.2.1 Inclusion Criteria

- Male or female, aged 21-60 years.
- A BMI categorized as overweight (≥ 25) but not stage II obesity (≤ 35)
- Daily steps < 5,000.

- Ownership of a smartphone device with either the Apple Health or Google Fit application.
- Willingness to carry their phone in their pocket or on their person at all times to track steps during study.
- Willing to download the Pro2col application and connect it with either the Apple Health or Google Fit application.
- Willingness to complete physical tasks including a timed one-mile walk/run, regular or modified push-ups to exhaustion, and chair get-ups to exhaustion.
- For the experimental group, subjects must be willing to follow the application protocol which is laid out later in this document.
- Able to read, understand, sign and date the informed consent document (English only)
- Able and willing to comply with the scheduled visit(s) and study requirements.

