10.3. Analyses

10.3.1 Primary Analysis

Descriptive statistics will be reported including mean, median, minimum and maximum values, standard deviation, and 95% confidence intervals of the mean. All outcome measure data will be reported as mean \pm standard deviation (SD). Relative and absolute changes between groups for all outcomes will be reported and analyzed for statistical significance using paired *t* tests. Additionally, effect sizes will be calculated as Cohen's d_g

for between-subjects analyses as the difference between group means divided by the pooled standard deviation times a correction factor [1]. Statistical significance will be set at p < 0.05 and all analyses will be performed using SPSS Version 28.0.

Cohen's
$$d_g = \frac{\left(X_{Group A} - X_{Group B}\right)}{SD_{pooled}} \times \left(1 - \frac{3}{4 \times (N1 + N2) - 9}\right)$$

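### The push-up form is neither recorded nor held constant within a subject, so a change of form between visits would count as a change in strength

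*Combined protocol and SAP*

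**What the plan says.** Section 4.1 makes push-ups one of three performance tests within a primary outcome: "Strength and Endurance, as assessed by performance measures including a timed mile walk/run, push-ups to exhaustion, and chair get-ups to exhaustion". Both sexes are enrolled ("Male or female, aged 21-60 years", section 5.2.1).

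Three places deal with the form of the test, and they differ:

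- Section 5.2.1 asks for willingness to do "regular or modified push-ups to exhaustion", without tying either form to sex.
- Sections 7.2 (baseline) and 7.4 (post-test) carry the same line: "Push-ups (or modified push-ups for women) to exhaustion". Modified push-ups are an alternative for women and are not offered to men.
- Appendix 1, under Strength and Endurance, says: "Users will be instructed via the application on correct form and technique for push-ups specific to their gender". It then takes one repetition count as the score: "This number will be reported to assess their upper body strength".

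Section 10.3.1 applies one summary to everything ("All outcome measure data will be reported as mean" with SD). It tests relative and absolute changes by t tests and adds a standardised effect size. It has no covariate, stratum or separate summary by sex or form.

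**The concern.** Regular and modified push-ups are different exercises, and a repetition count on one is not interchangeable with a count on the other. Two consequences follow.

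The first is within a subject. If the form at post-test differs from the form at baseline, the difference between the two counts mixes a change in strength with a change of exercise. Because the form is not recorded, such subjects could not be identified afterwards. Adjusting for baseline would not help them, since their baseline was taken on another exercise.

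The second is across subjects. One mean and one SD are reported for counts from two exercises, which makes the summary hard to interpret and can widen its spread.

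**Working it through.** The plan gives no push-up mean, SD or switching rate, so it has no figure of its own to reproduce here. The sample size of 50 in section 10.1 was set on habits like daily steps and does not depend on this point.

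**Step 1: can a compliant subject change form?** Set the sections side by side for a woman:

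| Place | Form allowed | Repeat of baseline form required? |
|---|---|---|
| 5.2.1 | Either | Not stated |
| 7.2 | Either (the modified form follows an *or*) | Not applicable |
| 7.4 | Either (same line) | Not stated |
| Appendix 1 | As taught by the app for her gender | Not stated |

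Under 7.2 and 7.4 she has the same choice at each visit, so regular at one and modified at the other breaks no rule. For a man, 7.2 and 7.4 give only the regular form while 5.2.1 mentions both.

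**Step 2: effect of a switch on mean change.** If a fraction q of an arm switches and each switch moves the count by s repetitions, the arm's mean change moves by q × s. The inputs q = 10% and s = 5 to 10 are assumptions.

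- 0.10 × 5 = 0.5 repetitions
- 0.10 × 10 = 1.0 repetition

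The sign depends on the direction of the switch. The between-arm difference moves by (q₁ − q₂) × s. With equal rates in the two arms it does not move in expectation, and switching only adds noise.

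**Step 3: effect of mixing forms on the spread of counts.** Assume a 50:50 mix of forms whose means lie δ within-form SDs apart. The pooled SD is multiplied by √(1 + δ²/4), and a standardised difference computed on counts is divided by the same factor.

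| δ (assumed) | SD factor | SD rise | d on counts shrinks by |
|---|---|---|---|
| 0.5 | 1.031 | 3% | 3% |
| 1.0 | 1.118 | 12% | 11% |
| 1.5 | 1.250 | 25% | 20% |
| 2.0 | 1.414 | 41% | 29% |

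**Step 4: does Step 3 reach the planned tests?** Write a subject's count as strength plus a form offset k.

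- *Absolute change, same form twice:* (post + k) − (baseline + k) = post − baseline. The offset drops out, so the factor is 1.00 at every δ.
- *Relative change, same form twice:* a gain g is scored as g/b on one form and g/(b + k) on the other. The offset does not drop out, so the result still depends on the form.
- *Effect size:* section 10.3.1 does not say whether the group means in the formula are counts or changes. Step 3 applies only if they are counts.

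**The case against.** The best defence is that the form is in effect fixed by sex. The line in 5.2.1 concerns willingness and may name both forms simply because both sexes enrol. Section 7 sends methodology to Appendix 1, which teaches "correct form and technique for push-ups specific to their gender", and the lines in 7.2 and 7.4 are identical. Gender is the same at both visits, so on a natural reading the form is too. This has weight and makes frequent switching less likely. It does not close the gap. Appendix 1 describes instruction on technique and does not state a rule on form, while 7.2 and 7.4 leave women an alternative. The instruction also comes through the app, and section 5.1 describes only the experimental group as enrolled in it, although 5.2.1 asks all subjects to be willing to download it. Strict assignment by sex would remove switching but would still leave two exercises in one mean and SD.

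A reader might infer that pooling costs 3% to 29% of the effect in the primary comparison. The plan does not support that, because it tests changes and a constant offset cancels in absolute change. Even for raw counts, the widening cannot be put down to form alone. If form follows sex, men and women might also differ on a common form, and a sex-specific form could narrow or widen that gap.

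A reader might also infer that coached subjects would move to the harder form more often, which would bias the comparison. Section 6.2 lists better exercise habits as a goal but describes no push-up progression or change of form. Differential switching is possible in an open, remote trial, but nothing in the documents establishes it or its direction.

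**Conclusion.** The point holds as a gap in how the test is specified. The sections disagree on who uses which form. No section records the form or requires it to be repeated, so a change of exercise can be counted as a change in strength. The illustrative size is 0.5 to 1.0 repetitions on an arm's mean change, resting entirely on an assumed 10% switching rate and a 5 to 10 repetition shift. The actual rate, and any difference between arms, is unknown.

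The 3% to 41% rise in SD applies to descriptive counts and to an effect size computed on counts, given an assumed 50:50 mix and a gap of 0.5 to 2 SD. It does not apply to the absolute-change test. Relative change stays dependent on the form. Turning these figures into lost power or a false-positive rate for push-ups would need inputs that the documents do not give.

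Severity is low: this is one of three tests within one of nine primary outcome domains in a pilot. It still merits correction before testing starts, because an unrecorded form cannot be reliably recovered later.

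**What to change.** - Reconcile sections 5.2.1, 7.2, 7.4 and Appendix 1 so that they state the same rule on which form is used and by whom, in both arms.
- Record the form at baseline and require the same form at post-test.
- For this measure, compare arms on post-test count with baseline count and sex (or form) as covariates, in place of the unadjusted t test on change.

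The cost is one data field, one line of instruction to subjects, and a covariate-adjusted model for this measure. Gender is already collected under section 10.2, but form is not. The sample size is unaffected. The model is a real change to the method in section 10.3.1 and should be written into the plan before data are analysed.
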